5.4. Subgroup analyses

The following subgroup analyses will be done:

Age: <5, 5-<18, 18-65, >65 years

Anti-viral treatment: Use of anti-viral treatment by the index case at randomisation. These include Paxlovid, Molnupiravir, Remdesivir and Favipiravir.

Number of SARS-CoV-2 exposures (vaccinations and infections) prior to the trial: 4 or less, vs > 4 Use any nasal treatment prior to coming into trial (Carrageenan or inhaled steroid, variables cm_flonasalspray_yn and cm_inhaledsteroids_yn)

Number of people in house: 2-3 vs > 3

Ratio of people to be drooms: < 1, 1, > 1

The subgroup analysis will be done by including an interaction term between the treatment arm and the subgroup in the model described in Section 5.1. For example,

xtpoisson outcome i.arm##i.subgroup baseline_covariates, re vce(robust) irr

The p-value of the subgroup by arm interaction term will be assessed to determine whether there could be a subgroup effect, with the understanding that the analysis is probably underpowered.

6. SECONDARY OUTCOMES

For all secondary outcomes referring to SARS-CoV-2 status we will use the algorithm as discussed in Section 3.8 and used for the primary outcome to determine SARS-CoV-2 infection status at any time point.

6.1 Secondary outcome 1. Efficacy of intranasal heparin to reduce SARS-CoV-2 viral shedding

To test the efficacy of intranasal heparin to reduce SARS-CoV-2 viral shedding over 10 days from day of positive swab (health professional collected swab day 3 and 5, and day 10)

Measure

1.1. Total number of index cases and household contacts combined (nasopharyngeal swab positive on day 1) who remain swab positive on day 3 according to health care provider collected swab

- 1.2. Total number of index cases and household contacts combined (nasopharyngeal swab positive on day 1) who remain swab positive on day 5 according to health care provider collected swab
- 1.3. Total number of index cases and household contacts combined (nasopharyngeal swab positive on day 1) who remain swab positive on day 10 according to health care provider collected swab

Estimand

Population: Household members who tested positive for SARS CoV-2 on day 1 on a nasopharyngeal swab PCR testing (health care provider collected swab)

Treatment: Initially randomised intervention to unfractionated intranasal heparin 1400u each nostril (as heparin solution 5,000u/ml, 140microL/actuation, TWO actuations each nostril) THREE times daily via a plastic nasal inhalator device or saline control and any subsequent deviations to the per protocol use of the intervention over 10 days

Outcome: Three different analyses will be done with 3 different outcomes

- a) Testing positive for SARS-CoV-2 by PCR on day 3 (using health care provider collected swab)
- b) Testing positive for SARS-CoV-2 by PCR on day 5 (using a health care provider collected swab)
- c) Testing positive for SARS-CoV-2 by PCR on day 10 (using a health care provider collected swab)

Summary measure: Both relative (risk ratio) and absolute differences (risk difference) in proportions will be reported with 95% confidence intervals

Potential intercurrent events:

Index case in the household not taking study drug. This is defined as compliance <90% Participant (this household member) not taking study drug. This is defined as compliance <90% Either participant (this household member) or index case stop treatment due to adverse event Participant hospitalisation during first 10 days (removed from household) Participant received an anti-viral

Strategy for handling intercurrent event:

All intercurrent events will be handled through the treatment policy strategy, which means that the intercurrent events will be ignored.

The same analysis as described in Section 5.1 for the primary outcome will be done. We will do the same sensitivity and supplementary analysis, but no subgroup analyses are planned.

Measure

1.4. Time to swab negative based on health care provider collected nasal swab for household members index cases and household contacts) who were swab positive on day 1 by PCR

Estimand

Population: Household members who tested positive for SARS CoV-2 on day 1 on a nasopharyngeal swab PCR **Treatment**: Initially randomised intervention to unfractionated intranasal heparin 1400u each nostril (as heparin solution 5,000u/ml, 140microL/actuation, TWO actuations each nostril) THREE times daily via a plastic nasal inhalator device or saline control and any subsequent deviations to the per protocol use of the intervention over 10 days

Outcome: Days from randomisation to the date of the first negative nasal swab. Participants who still test positive on day 10 will be censored on day 10 and regarded as not testing negative.

Summary measure: Median time to first negative test in each treatment arm. Hazard ratio.

Potential intercurrent events:

Index case in the household not taking study drug. This is defined as compliance <90% Participant (this household member) not taking study drug. This is defined as compliance <90% Either participant (this household member) or index case stop treatment due to adverse event Participant hospitalisation during first 10 days (removed from household) Participant received an anti-viral

Strategy for handling intercurrent event:

All intercurrent events will be handled through the treatment policy strategy, which means that the intercurrent events will be ignored.

Days to first negative test will be calculated from baseline to the first negative PCR tests within the first 10 days after randomisation. Participants who still test positive at the last time point will be censored at the time

of last test. Participants who are lost to follow-up without testing negative, will be censored at the time of the last positive test. The days to negative test will be compared between the two treatment arms using a proportional hazards models with clustered standard errors [using vce(cluster) in Stata]. The model will be adjusted for the same set of defined baseline covariates (Section 5.1). Days to negative test will be summarised by reporting the median, with 95% confidence interval.

Measure

1.5 Mean Ct values on days 3, 5 and 10

Estimand

Population: Household members who tested positive for SARS CoV-2 on day 1 on a nasopharyngeal swab PCR **Treatment**: Initially randomised intervention to unfractionated intranasal heparin 1400u each nostril (as heparin solution 5,000u/ml, 140microL/actuation, TWO actuations each nostril) THREE times daily via a plastic nasal inhalator device or saline control and any subsequent deviations to the per protocol use of the intervention over 10 days

Outcome: The mean Ct value at each time point on all genes (E, N, RdRp/S gene). Ct value for the virus that was not detected will be set at the maximum number of cycles performed in the lab (40). **Summary measure**: The mean difference between arms will be reported with 95% confidence interval **Potential intercurrent events**:

Potential intercurrent events:

Index case in the household not taking study drug. This is defined as compliance <90% Participant (this household member) not taking study drug. This is defined as compliance <90% Either participant (this household member) or index case stop treatment due to adverse event Participant hospitalisation during first 10 days (removed from household) Participant received an anti-viral

Strategy for handling intercurrent event:

All intercurrent events will be handled through the treatment policy strategy, which means that the intercurrent events will be ignored.

Treatment arms will be compared using mixed effects linear regression with Ct value as the outcome, adjusting for stratification factors (time from positive test to randomisation, whether the index case is a child < 5 years), participant age, inhaled steroid use at baseline, days since symptom onset at randomisation, whether there are children in the household and household size (referred to as the defined baseline covariate set), with household as random effect to take the clustering by household into account.

Measure

1.6 Lowest Ct value amongst household members who become positive during the first 10 days

Estimand

Population: Household members who tested negative for SARS CoV-2 on day 1 on a nasopharyngeal swab PCR and subsequently become SARS CoV-2 positive during the first 10 days

Treatment: Initially randomised intervention to unfractionated intranasal heparin 1400u each nostril (as heparin solution 5,000u/ml, 140microL/actuation, TWO actuations each nostril) THREE times daily via a plastic nasal inhalator device or saline control and any subsequent deviations to the per protocol use of the intervention over 10 days

Outcome: The mean Ct value at each time point at or after the first positive SARS-CoV-2 test on all genes (E, N, RdRp/S gene). Ct value for the virus that was not detected will be set at the maximum number of cycles performed in the lab (40). For each participant the lowest Ct value detected at or after the first positive test will be used.

Summary measure: The mean difference between arms will be reported with 95% confidence interval

Treatment arms will be compared using mixed effects linear regression with lowest Ct value as the outcome, adjusting for the defined baseline covariate set, with household as random effect to take the clustering by household into account.

The mean difference between the treatment arms will be calculated in Stata as follows using a mixed effects GLM:

mixed outcome i.arm baseline_covariates || household:

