5.3. Supplementary analyses

We define a supplementary estimand, through handing the intercurrent event of not taking study drug differently.

Supplementary estimand

Population: Household contacts who test negative for SARS CoV-2 on day 1 (baseline) PCR testing using the health care provider swabs

Treatment: Unfractionated intranasal heparin 1400u each nostril (as heparin solution 5,000u/ml, 140microL/actuation, TWO actuations each nostril) THREE times daily via a plastic nasal inhalator device or saline control

Outcome: Testing positive for SARS-CoV-2 by PCR on any of three health care provider collected swabs at days 3, 5 and 10 while participant and index case do not discontinue treatment due to adverse events. The algorithm to determine SARS-CoV-2 positivity is described in detail in Section 3.8. If one of the post-baseline swabs is missing, but all observed swabs were negative, the participant will be regarded to be negative. If more than one post-baseline swab is missing and the observed swabs were all negative, the outcome will be regarded to be missing.

Summary measure: Both relative (risk ratio) and absolute differences (risk difference) in proportions will be reported with 95% confidence intervals

Potential intercurrent events:

Index case in the household not taking study drug. This is defined as compliance <90% Participant (this household member) not taking study drug. This is defined as compliance <90% Either participant (this household member) or index case stop treatment due to adverse event Participant hospitalisation during first 10 days (removed from household) Participant received an anti-viral

Strategy for handling intercurrent event:

Index case in the household not taking study drug. This is defined as compliance <90%: This intercurrent event will be handled following the hypothetical strategy. For index cases who used <90% of study drugs we will set all SARS-CoV2 infections observed in the household to missing. We will use multiple imputation to impute these outcomes.

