Participant (this household member) not taking study drug. This is defined as compliance <90%: This intercurrent event will be handled following the hypothetical strategy. We will set all SARS-CoV2 infections observed to missing. We will use multiple imputation to impute these outcomes. Either participant (this household member) or index case stop treatment due to adverse event: We will handle this intercurrent event using the while on treatment strategy. We will do this by excluding outcomes after participants stop study treatment due to adverse events from the analysis. All other intercurrent events will be handled by using the treatment policy strategy, which means that those intercurrent events will be ignored.

This analysis will only be done if more than 7% of participants had the intercurrent events.

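### For Measures 1.1-1.3, the inherited supplementary analysis can set a compliant day 1-positive contact's positive results to missing because the index case missed doses

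*SAP*

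**What the plan says.** SAP Section 6.1 defines the population for Measures 1.1-1.3 as "Household members who tested positive for SARS CoV-2 on day 1 on a nasopharyngeal swab PCR testing", with index cases and contacts pooled. All intercurrent events are handled by treatment policy in the main analysis. The section then adds: "We will do the same sensitivity and supplementary analysis, but no subgroup analyses are planned". It does not adapt anything. Table 10 has a hypothetical-estimand row for these measures.

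The supplementary analysis itself is in Section 5.3. Its population is "Household contacts who test negative for SARS CoV-2 on day 1 (baseline) PCR testing using the health care provider swabs". Its index-case rule is "For index cases who used <90% of study drugs we will set all SARS-CoV2 infections observed in the household to missing", followed by "We will use multiple imputation to impute these outcomes". The participant's own non-use is a separate event with its own rule: "Participant (this household member) not taking study drug. This is defined as compliance <90%: This intercurrent event will be handled following the hypothetical strategy". A stop for an adverse event, by either the participant or the index case, is handled while on treatment. The whole analysis is run only if more than 7% of participants had the events.

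**The concern.** In the primary outcome the index case is the presumed source. Whether that person used the drug can change a negative contact's exposure, so a hypothetical strategy for index-case non-use has a rationale. Measures 1.1-1.3 ask something else: does a person who is already positive on day 1 stay positive? The SAP gives no reason why another household member's missed doses should decide whether that person's clearance data count.

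Two things are at stake in the supplementary shedding estimate. First, observed results from compliant participants are replaced by imputations, which costs precision and makes the estimate less relevant to drug use by the person being swabbed. Second, Section 5.3 speaks of infections being set to missing. For shedding, a positive swab is the event being counted, so a literal application removes events and keeps non-events.

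**Working it through.** **Step 1. The two sections side by side (SAP).**

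| Item | Section 5.3 | Section 6.1, Measures 1.1-1.3 |
|---|---|---|
| Population | Day 1-negative contacts | Day 1-positive index cases and contacts |
| Event counted | Becoming positive | Remaining positive |
| Index case under 90% | Household infections set to missing, imputed | Inherited unchanged |
| Own compliance under 90% | Separate event, infections set to missing, imputed | Inherited unchanged |

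Because the two compliance events are separate, the index-case rule applies whatever the contact's own compliance. The Section 5.3 population cannot be carried over at all, since nobody in Measures 1.1-1.3 was negative on day 1.

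**Step 2. What triggers the rule.** Section 4.4 counts doses on days 3 to 10, with 24 as the denominator. 22/24 = 91.7% and 21/24 = 87.5%, so with a complete diary three missed doses put a person below 90%. Each day without diary data lowers the denominator by 3. With two such days, 16/18 = 88.9%, so two missed doses suffice.

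**Step 3. How many compliant contacts could be flagged.** The SAP gives no compliance rates, so this is an illustration. Assume index case and contact each fall below 90% with probability q, independently. Then:

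- compliant contacts flagged through the index case = q(1 - q)
- contacts flagged for either reason = 1 - (1 - q)²

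| q | Compliant but flagged | Flagged for either reason | Compliant share of those flagged |
|---|---|---|---|
| 5% | 4.75% | 9.75% | 48.7% |
| 10% | 9% | 19% | 47.4% |
| 20% | 16% | 36% | 44.4% |
| 30% | 21% | 51% | 41.2% |

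These are shares of day 1-positive contacts. For an index case the two compliance rules coincide, so no index case is flagged through someone else. If contacts are a fraction c of the pooled population, the pooled share is c × q(1 - q), which is smaller. The SAP does not give c.

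**Step 4. The literal wording.** Assume a share p = 0.60 is positive at a given visit (not an SAP figure), a fraction f of participants is flagged, and positivity does not differ by flag. If only the flagged positives are removed, the positive share among the results left, before imputation, is p(1 - f) / [p(1 - f) + (1 - p)]:

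- f = 10%: 0.54/0.94 = 57.4%
- f = 20%: 0.48/0.88 = 54.5%
- f = 30%: 0.42/0.82 = 51.2%

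Every flagged participant's remaining result is negative. Section 3.7 puts predictors of missingness into the imputation model. If that model is used here and includes the compliance flag, it has no observed positives among flagged people from which to recover those removed.

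**Step 5. The adverse-event rule.** Section 5.3 names a stop by the participant or by the index case as the event. Its operating sentence, however, excludes outcomes after participants stop. Whether an index case's stop also truncates another person's shedding results cannot be settled from the text.

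**The case against.** The strongest reply is that little depends on this. The main analysis of Measures 1.1-1.3 ignores intercurrent events, and the supplementary one is conditional on the 7% threshold. That is correct and sets the limit of the point. A reader might infer that the principal shedding result loses data; the SAP does not support that.

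Second, households are randomised and treated as units, so a hypothetical in which participant and index case both adhere is a coherent estimand. Section 6.1 also lists index-case non-use among its intercurrent events. Part of this stands: it is a choice of estimand, not an arithmetical error. But the same list recurs for nearly every outcome, so it is weak evidence of a deliberate choice. The rule was written for a different population and event, and the SAP's clarification of terms says that index cases are not analysed separately from other members.

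Third, some stronger readings are tempting but go beyond the text:

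- That all of a compliant contact's day 3, 5 and 10 results are replaced. Section 5.3 refers to infections, so literally only positives are.
- That an index case's adverse-event stop certainly cuts off the contact's data. The text is ambiguous.
- That every household with an index child under 5 is flagged by design, because such children are untreated (Section 2.3). The SAP leaves that child's compliance undefined.
- That the affected share is larger. Taking 20-40% index non-compliance and 50-80% compliance among contacts in those households gives 0.20 × 0.50 = 10% to 0.40 × 0.80 = 32%, but the SAP supports neither input.

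**Conclusion.** The point holds for the supplementary analysis only. Section 6.1 imports a rule made for transmission to negative contacts, and under it a compliant day 1-positive contact's positive results can be set to missing and imputed because of another person's dosing. If the wording is applied literally, the missingness also depends on the outcome, so bias is a risk as well as lost precision.

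The reach is the hypothetical-estimand row of Table 10, and only when the 7% condition is met. The true share of contacts affected cannot be derived from the SAP. The figure of about 5-21% of day 1-positive contacts rests on independent and equal non-compliance of 5-30%, and the share of the pooled population is lower. The change is worth making because it is nearly free and the analysis is already planned for reporting.

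**What to change.** In Section 6.1, replace the reference to the Section 5.3 supplementary analysis with a short estimand for Measures 1.1-1.3 that states:

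- the population is household members positive on day 1;
- the hypothetical strategy applies only to the participant's own compliance below 90%;
- the while-on-treatment strategy applies only to the participant's own adverse-event stop;
- for non-compliant participants, the affected day 3, 5 and 10 results are set to missing whether positive or negative, then imputed.

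Index cases stay covered because they are participants themselves. Dropping the index-case events alone would not be enough: the negative-contact population and the wording about infections would remain, the latter also for the participant's own non-use. The cost is one short paragraph. It needs no new data and no added analysis, and it keeps observed results from compliant participants.

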2.7 Study procedures

When a participant is confirmed to be SARS-CoV-2 positive all consenting household members are enrolled and randomised to the same treatment arm. All consenting household members 5 years of age and older will be given the same study treatment. Treatment is 10 days and follow up for primary outcome is 10 days. Follow up for some secondary outcomes are 28 days and outcomes related to long COVID is 6 and 12 months post randomisation.

Daily communication via SMS, online or phone will be conducted by a research team member who will be trained in standard operating procedures as per trial manual. Paediatric or adult swabs (Rhinomed) will be provided to all participants with detailed instructions for self-collection and storage until collected by a research team member. Health care provider collected PCR nasopharyngeal swabs will be collected from all participants prior to commencement of study medication and on day 3, 5 and 10 (+/- 1 day for all time points).

Phone call follow up at day 14 and 28 by a research team member will assess which participants became symptomatic after the initial treatment period and whether participants required hospitalisation during that time. Detailed medical information as to reasons for hospital admission will be sought to confirm if admission was related to COVID-19 infection or for alternative reasons. Research team members will be trained specifically in questions to ask according to trial manual, which will include an escalation process if a research team member believes that additional clinical care is required for the participant or family member.

Telemedicine follow up at day 180 +/- 10 days and day 365 +/- 10 days to ascertain any evidence of long COVID neurological symptoms.

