2.8 Deviations from protocol

Secondary measures 1.5 and 1.6 were not specified in the protocol, but were added to the statistical analysis plan.

Reference to consecutive daily swabs were removed, since only the healthcare provider swabs are used and they are not collected daily.

No other large deviations from the protocol occurred. Where the text deviates from the protocol, the changes were made to resolve inconsistencies and ambiguities, without the intention of diverging from the original protocol.

Full details of the background to the trial and its design are presented in the protocol.

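### Measure 1.4 treats the date of the first negative swab as an exact clearance time, so its hazard ratio is understated if heparin truly speeds clearance

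*SAP*

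**What the plan says.** Section 6.1 defines the outcome of Measure 1.4 as "Days from randomisation to the date of the first negative nasal swab". On censoring it states: "Participants who still test positive on day 10 will be censored on day 10". The summary measure is given as "Median time to first negative test in each treatment arm. Hazard ratio". The arms are compared with "proportional hazards models with clustered standard errors", adjusted for the baseline covariate set.

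The data behind this come from Section 2.7, where provider swabs are taken "prior to commencement of study medication and on day 3, 5 and 10 (+/- 1 day for all time points". Section 2.8 explains why daily swabs were dropped from the text: "only the healthcare provider swabs are used and they are not collected daily".

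For Measure 1.4 the SAP names no tie method, no interval-censored or grouped-time model, and no sensitivity analysis on this point. It gives no Stata command beyond the clustered variance option.

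**The concern.** A participant who is positive on day 5 and negative on day 10 cleared at some point in those five days. With both swabs at the far ends of their windows (days 4 and 11), the gap is seven days. The analysis enters the right-hand end of the interval as if it were the clearance time.

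Two things follow. First, many participants share the same few event dates. The Breslow approximation then compares the shares turning negative at each visit, and that ratio lies closer to 1 than the ratio of hazards. Second, the +/-1 day window spreads the event dates for reasons unrelated to clearance, and an exact-time model reads that spread as information.

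At stake is the size of the reported effect on duration of shedding, and whether its 95% interval covers the true value as often as it should.

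**Working it through.** **Inputs.** From the SAP: swab days 3, 5 and 10, each +/-1 day (2.7); event at the first negative swab, censoring at day 10, and a proportional hazards model with clustered errors (6.1); 1:1 allocation by household (2.5). The SAP has no sample size, event count or expected HR for Measure 1.4, since Section 2.6 sizes the primary outcome only. There is thus no planned figure to reproduce. Clearance patterns, true HRs and tie methods below are assumptions.

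**Step 1: direct calculation, exact visit days, true HR 1.5.** Assume 10/30/70% of controls have cleared by days 3/5/10, so the shares still positive are 0.9, 0.7 and 0.3. Under proportional hazards the heparin share still positive is the control share to the power 1.5. The chance of turning negative at a visit, given still positive before it, is 1 - S(visit)/S(previous visit).

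| Visit | Control | Heparin | Ratio |
|---|---|---|---|
| Day 3 | 0.100 | 1 - 0.9^1.5 = 0.146 | 1.46 |
| Day 5 | 1 - 0.7/0.9 = 0.222 | 1 - 0.7778^1.5 = 0.314 | 1.41 |
| Day 10 | 1 - 0.3/0.7 = 0.571 | 1 - 0.4286^1.5 = 0.719 | 1.26 |

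The Breslow estimate θ makes observed heparin negatives equal expected ones: Σ d1 = Σ (d0 + d1) × r1θ/(r1θ + r0), with r the shares at risk and d the shares turning negative.

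- Control: r0 = 1, 0.9, 0.7 and d0 = 0.10, 0.20, 0.40.
- Heparin: r1 = 1, 0.854, 0.586 and d1 = 0.146, 0.268, 0.421, which sum to 0.836 before rounding.
- At θ = 1.335 the right side is 0.141 + 0.262 + 0.433 = 0.836.

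The true 1.5 is therefore estimated as 1.33. The same calculation gives 1.29 for control clearance of 15/40/85% and 1.42 for 5/10/35%.

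The complementary log-log scale recovers the truth at every visit. At day 10, for example, ln(0.2806)/ln(0.4286) = 1.2709/0.8473 = 1.50.

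**Step 2: simulation with and without the visit window.** Each scenario had 100,000 participants, Weibull clearance times (shape 1 or 2) and 40, 60 or 80% of controls cleared by day 10. Swabs fell on fixed days or were shifted by -1, 0 or +1 day. Ranges run across scenarios.

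| True HR | Breslow, fixed or window | Efron, fixed | Efron, +/-1 day | Grouped log-log |
|---|---|---|---|---|
| 1.3 | 1.16-1.26 | 1.25-1.30 | 1.22-1.28 | 1.28-1.31 |
| 1.5 | 1.26-1.45 | 1.42-1.51 | 1.35-1.49 | 1.48-1.52 |
| 2.0 | 1.49-1.86 | 1.82-2.00 | 1.66-1.96 | 1.97-2.02 |

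With a true HR of 1.0 every method gave 0.99-1.01. The attenuation is about 2-26% of the HR under Breslow ties and negligible to about 18% under Efron ties. It grows with the share cleared by day 10 and with the true HR.

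**Step 3: interval coverage.** Assume 180 day-1 positives per arm, control clearance of 10/30/70% or 15/40/85%, robust errors and no household effect, with 600 replicates. For a true HR of 1.5, the nominal 95% Breslow interval covered the truth in 46-76% of runs on fixed days and 73-87% with +/-1 day dates. The complementary log-log model covered 94-96%.

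**Step 4: power.**

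- In the Step 3 set-up with +/-1 day dates, Breslow against complementary log-log gave 47-49% against 55-57% at HR 1.3, and 84-85% against 92-95% at HR 1.5. On fixed days the loss was at most 3 points.
- With 100 households per arm, two positives each, and a household effect (SD 0.5 on the log hazard), power at HR 1.5 with +/-1 day dates was 77% against 80% (10/30/70% clearance), 78% against 82.5% (15/40/85%) and 61% against 61.5% (5/10/35%). On fixed days it was 85% against 83%, 86% against 85% and 61.5% against 62%. Monte Carlo error is about 3 points per figure.

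**The case against.** **The tie method is open.** The larger attenuation assumes Breslow ties, which the SAP does not specify. Under Efron ties on fixed days a true 1.5 is estimated at 1.42-1.51, which is close. This limits the size but does not remove the point: with the SAP's own visit window Efron still gives 1.35-1.49, and the shortfall is clearest when most participants clear by day 10.

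**A real shortening might be thought likely to be missed.** The documents and the checks do not support that. The smaller coefficient comes with a smaller robust standard error, and the power loss runs from none to about 10 points across the two sets of runs. With no bias at a true HR of 1, there is no sign of a false-positive problem either.

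**The shedding objective as a whole might be thought understated.** It is not. Measures 1.1-1.3 analyse positivity at each visit as a binary outcome, and Measures 1.5 and 1.6 use Ct values. None of them depends on event times.

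**The median might be called wrong because it falls on a swab day.** It is the quantity that Section 6.1 defines, so this is a matter of labelling.

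**The target could be the date of detection itself.** Even so, the single HR has no clean meaning. In Step 1 the visit-specific ratios fall from 1.46 to 1.26 although the underlying HR is constant, so the fitted value depends on the swab schedule.

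**Conclusion.** The point holds for the hazard ratio in Measure 1.4. If heparin speeds clearance, the planned model understates by how much. With 35-85% of controls cleared by day 10, a true HR of 1.5 becomes about 1.3-1.45 under Breslow ties, and about 1.35-1.5 under Efron ties with the +/-1 day window. Lower clearance gives less attenuation.

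The direction was consistent when there was a true effect: Breslow estimates were always below the continuous-time HR, and Efron estimates at or below it. The size depends on clearance rates, a true HR and a tie method that the SAP does not give. The coverage figures also assume 180 positives per arm, Breslow ties and no household effect. They will be milder where clearance is lower or households are strongly correlated.

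This is a secondary measure with an avoidable, one-directional error in effect size and interval. It is worth correcting, but it does not threaten the primary analysis or the other shedding measures.

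**What to change.** In Section 6.1, replace the Measure 1.4 model with one of these:

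- an interval-censored proportional hazards model, with each participant's interval running from the last positive to the first negative provider swab date, and right-censoring at the last positive swab; or
- a discrete-time complementary log-log model with visit indicators.

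Either should use household-clustered standard errors and the Section 3.9 covariates. The first uses actual swab dates and accommodates a missed visit directly.

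The median may stay if labelled as time to first detected negative swab and read beside the by-visit proportions already planned in Measures 1.1-1.3. Section 6.3 borrows the Measure 1.4 analysis for symptom resolution, which comes from a daily diary. A sentence there should say which model applies.

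The cost is one different model and some SAP wording. No new data are needed, and the HR still compares the rate of clearance between arms.
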